1.7 HOW THE TRIAL MIGHT IMPACT ON CLINICAL PRACTICE

The trial results will inform patients, clinicians, international practice guidelines, and payers as to the pros and cons of CABG vs. PCI in patients with iLVSD requiring coronary revascularisation. Results from this trial will be generalisable to a large proportion of patients with advanced iLVSD and will inform Heart Team discussions and appropriateness of care. If CABG has a survival advantage over PCI, it will remain the preferred strategy for revascularisation in Heart Team discussions and reduce the number of non-evidence-based PCIs. If CABG is not superior to PCI, the results have the potential to minimise the early mortality and mortality hazards associated with CABG and to facilitate the access to revascularisation in a growing population of patients with HfrEF.

RESEARCH QUESTION/AIM(S)

1.8 HYPOTHESIS

CABG is superior to PCI in terms of primary and secondary clinical and cost-effectiveness outcomes in people with iLVSD.

1.9 OBJECTIVES

1. STICH3-BCIS4 will compare PCI versus CABG for the revascularisation of patients with iLVSD, defined as left ventricular ejection fraction (LVEF) \leq 40% and multivessel coronary artery disease.
2. An internal pilot will test design assumptions around recruitment at 12 months.
3. A health economic analysis will determine cost-effectiveness.
4. A PPI researcher led work package will improve recruitment in underserved groups.
5. The trial will contribute data to the international STICH-3 analysis that will evaluate the comparative effectiveness of CABG versus PCI in iLVSD for the outcome all-cause mortality.

1.10 OUTCOME

The trial will be considered positive if the time-to first event for the primary outcome of all-cause mortality or cardiovascular hospitalisation is superior (longer) in the CABG arm (intervention) versus the PCI (control) arm at the 5% (two-sided) statistical significance level with a HR of less than or equal to 0.7.

TRIAL DESIGN

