1.16 SIZE OF SAMPLE

STICH3-BCIS4 is a superiority trial powered for the primary outcome of survival time from cardiovascular hospitalisation and all-cause mortality. Using a time-to-event analysis to detect a HR of 0.7 with a 1:1 allocation ratio, 90% power, and a 2-sided alpha value of 0.05, a total of 414 events are required. Participants will receive a minimum of 4 years follow-up and 630 participants (n=315 in each arm) will be randomised in the UK.

The sample size is based on the following assumptions. **1.** A minimum clinically important treatment effect HR for CABG vs. PCI of 0.7 that is written within the range of treatment effects (0.63 to 0.74) observed in previous pragmatic RCTs of CABG versus PCI that have changed clinical practice (20-22). The proposed effect size was chosen as stakeholders felt that a large benefit would be required to convince clinicians of the benefits of more invasive treatment (CABG) in this high-risk population. **2.** Frequency of death or cardiovascular hospitalisation of 70% at 5 years in the PCI arm, from HES. To

calibrate this outcome, we compared the frequency of death or *heart failure* hospitalisation at 5 years in the STICH-1 matched HES cohort (42%) to event rates in both REVIVED and STICH trials (see Figure 1, from reference (8)). As heart failure hospitalisation is underestimated in HES data, the expected outcome frequencies are consistent. Coding for CV hospitalisation is more accurate and is included in the primary outcome for STICH3-BCIS4. **3.** A total study period of 89 months. **4.** An expected crossover rate of 8% typical for CABG vs. PCI trials; range 7-9%. (6, 7). **5.** Zero attrition due to the use of HES / Office for National Statistics (ONS) data for the primary outcome.

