1.26 METHOD OF IMPLEMENTING THE RANDOMISATION/ALLOCATION SEQUENCE

1.26.1 Randomisation

Randomisation with allocation concealment will utilise a centralised, web-based system (Sealed Envelope Ltd, London, UK). Participants will be randomised on the day of consent in a 1:1 ratio to either CABG or PCI stratified by centre and clinical presentation; acute versus chronic coronary syndrome.

The participant's initials, date of birth, and sex will be entered into the randomisation system which will generate the participant's randomised allocation (PCI or CABG) and unique participant identifier (Trial ID).

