1.46 PRIMARY OUTCOME ANALYSES

The primary outcome (all-cause mortality or cardiovascular hospitalization) will be calculated by measuring time from randomisation until first event or last known event-free observation during the follow-up period as defined in 1.17.1. The primary analysis of the primary outcome will compare the randomised groups using a log-rank test statistic. Survival estimates will be presented using methods by Kaplan and Meier and the adjusted hazard ratio and 95% confidence interval presented using a cox proportional hazards model (or appropriate alternative where assumptions are not met). Superiority of CABG over PCI will be declared with a two-sided p-value <0.05 on the log-rank test. A secondary analysis of the primary outcome will follow the same methodology on the per protocol (PP) population.

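### Section 1.10 requires HR ≤0.7 for a positive trial while 1.46 requires only p<0.05; the stated 90% power applies to 1.46, and under 1.10 it is about 50% or lower

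*Protocol*

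**What the plan says.** The protocol fixes the success criterion for the primary outcome (time to first cardiovascular hospitalisation or death from any cause) in two places.

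- Section 1.10 says when the trial counts as positive: CABG must be superior "at the 5% (two-sided) statistical significance level with a HR of less than or equal to 0.7". As worded, this is a joint condition on the p-value and the hazard ratio.
- Section 1.46 says: "Superiority of CABG over PCI will be declared with a two-sided p-value <0.05 on the log-rank test". It reports the HR with a confidence interval but sets no threshold for it.

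Section 1.16 sizes the trial "to detect a HR of 0.7 with a 1:1 allocation ratio, 90% power, and a 2-sided alpha value of 0.05", and on that basis "a total of 414 events are required", from 630 participants. It describes the value as "A minimum clinically important treatment effect HR for CABG vs. PCI of 0.7". It assumes 8% crossover without giving a direction, and 1.58.5 confirms that crossover is built into the sample size. The sample-size and analysis rows of the Study Summary carry no HR threshold for success.

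**The concern.** The two rules give different answers over a range of results that the trial is quite likely to produce. An observed HR of 0.75 with 414 events would have a p-value of about 0.003. Under 1.46 CABG would be superior; under 1.10 the trial would not be positive. Section 1.16 itself cites effects of 0.63 to 0.74 from trials that it says changed practice, and an observed 0.74 here would also fail 1.10.

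The power statement is affected too. A design effect is a value that the trial should be able to tell apart from no effect. When the same value becomes a threshold for the estimate, an estimate centred on it misses about half the time. A reader who takes 1.10 as the success rule and 1.16 as its power would believe that a true HR of 0.7 gives a 90% chance of a positive trial, which is not so.

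**Working it through.** **Inputs.** From 1.16: HR 0.7, two-sided alpha 0.05, power 90%, 1:1 allocation, 414 events, 8% crossover, 70% event rate at 5 years in the PCI arm. From 1.20: 41 months of recruitment. The direction of crossover is not stated. I assume that 8% of the CABG arm has the PCI hazard and show an alternative below.

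**Step 1. Reproduce the 414 events.** With (1.960 + 1.282)² = 10.507:

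- Schoenfeld, D = 4 × 10.507 / (ln HR)². At HR 0.70 this is 42.03 / 0.1272, or 331 events.
- Freedman, D = 10.507 × [(1 + HR)/(1 − HR)]². At HR 0.70 this is 338 events.

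Neither matches 414, so crossover must have been added. Diluted HR = 0.92 × 0.7 + 0.08 = 0.724. Schoenfeld then gives 403 and Freedman 410, both within 3% of 414. The stated size is therefore approximately reproduced, for a test that needs only p<0.05.

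**Step 2. Find which condition binds at 414 events.** SE(log HR) = 2/√414 = 0.0983. Significance in favour of CABG needs an observed HR ≤ exp(−1.96 × 0.0983) = 0.825. Since 0.70 is the stricter limit, it alone decides the 1.10 rule.

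The 0.70 limit is the stricter one whenever 1.96 × 2/√D < 0.3567, that is, above about 121 events. In that range the 50% in Step 3 does not depend on the number of events.

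**Step 3. Compute power under each rule.**

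- 1.46: Φ((−1.96 × 0.0983 − ln HR)/0.0983)
- 1.10: Φ((ln 0.7 − ln HR)/0.0983)

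| True HR | Power, 1.46 | Power, 1.10 | Chance that the rules disagree |
|---|---|---|---|
| 0.70 (design value) | 95.2% | 50.0% | 45.2% |
| 0.724 (8% crossover, CABG arm) | 90.8% | 36.6% | 54.2% |

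The last column is the difference between the two powers, because every result that meets 1.10 also meets 1.46.

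**Step 4. Check by simulation.** I used 4,000 trials per case, exponential survival, uniform accrual over 41 months, analysis at the 414th event, and a log-rank test with a Cox HR. Power at HR 0.70 was 95.6% (1.46) and 49.4% (1.10). At HR 0.724 it was 91.0% and 36.5%.

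**Step 5. Find the true HR at which 1.10 has 90% power.** exp(ln 0.7 − 1.2816 × 0.0983) = 0.617. This lies below the whole 0.63 to 0.74 range quoted in 1.16.

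**Step 6. Check the example.** At an observed HR of 0.75, z = ln 0.75 / 0.0983 = −2.93, two-sided p ≈ 0.003.

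**The case against.** The best defence is that the HR phrase in 1.10 only restates the design effect. Section 1.46, where the analysis is defined, is unambiguous. The opposite defence is that the hurdle is deliberate. Section 1.16 reports that stakeholders wanted a large benefit before accepting the more invasive treatment, so superiority in 1.46 and a positive trial in 1.10 could be two separate levels of success. Either is plausible, and the protocol does not say which is meant. Neither removes the problem: on the first reading the phrase is misplaced, and on the second the 90% power does not apply to it.

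Some stronger readings are tempting but not supported:

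- **The rule can be chosen after seeing the data.** The opening of the Statistical Analysis section requires a SAP to be final before any analysis by treatment group. The text is inconsistent, but it does not license a post-hoc choice.
- **The trial is too small.** For the 1.46 rule, 414 events give the stated power under CABG-arm crossover.
- **Power under 1.10 is only 28%.** That follows from 8% crossover in both arms (HR 0.742). That pattern needs 472 (Schoenfeld) or 479 (Freedman) events, so it is not what produced 414.
- **The deciding log-rank test ignores the stratified randomisation.** Section 1.46 does not say that the test is unstratified, and 1.50 ties the adjustment variables to data required at randomisation. Whether the test is stratified, and how centre is modelled, can properly be left to the SAP.

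**Conclusion.** The contradiction stands and concerns the primary success criterion, so it needs correcting. At 414 events, power under 1.10 is about 50% at a true HR of 0.70 and about 37% at 0.724, against 95% and 91% under 1.46. The rules conflict for every significant result with an observed HR above 0.70 and up to about 0.825.

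The 50% rests only on an estimate centred on the true value and on the limit of 0.70 being stricter than the significance limit, which holds easily here. The 37% also assumes crossover confined to the CABG arm, which the protocol does not state. The finding does not depend on that assumption, because any dilution towards 1 pushes power under 1.10 below 50%. Recruitment, data collection and the sample size for the 1.46 rule are not called into question.

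**What to change.** Reconcile 1.10, 1.16 and 1.46 into one rule.

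- **Preferred:** delete the HR condition from 1.10, so that both sections define success as a two-sided log-rank p-value below 0.05 favouring CABG. Keep 0.7 in 1.16 as the design alternative, and judge clinical importance from the HR and its 95% confidence interval. The 414 events and 90% power then stand as written.
- **If the HR condition is intended:** state it in 1.46 as well, and restate the power in 1.16 as about 50% at a true HR of 0.70, and lower once crossover is allowed for.

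The preferred option costs a one-sentence protocol amendment with matching SAP wording, and the alternative a few sentences more. Neither needs more participants or data. The change should be made before the SAP is finalised and before any analysis by treatment group.

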1.11 TRIAL DESIGN

Multicentre, open label, parallel group, RCT of two common revascularisation strategies in people with iLVSD, using a superiority design, with embedded internal pilot, and health economic analysis.

1.12 TRIAL SETTING

At least 28 tertiary cardiac centres in the UK will recruit to STICH3-BCIS4. Over 100 international sites will recruit to STICH-3.

1.13 PARTICIPANTS

1.13.1 Target Population

Patients with multivessel disease, a documented indication for revascularisation, who are deemed by the local Heart Team to be appropriate and suitable for revascularisation by either PCI or CABG and meet all the eligibility criteria.

1.14 ELIGIBILITY CRITERIA

1.14.1 Inclusion Criteria

1. Age ≥ 18 years
2. LVEF $\leq 40\%$ (quantified by any recognised imaging modality) within the last 12 months. If the patient has had an MI within the last 12 months post-MI imaging is required with LVEF $\leq 40\%$
3. Significant amount of myocardium at risk defined as coronary artery disease with BCIS myocardial jeopardy score ≥ 6 on recent (< 6 months) coronary angiogram
4. Signed informed consent

1.14.2 Exclusion Criteria

5. Decompensated heart failure requiring inotropic support, invasive or non-invasive ventilation or mechanical circulatory support less than 48 hours prior to randomisation

6. ST Elevation Myocardial Infarction (STEMI) <72 hours
7. Valvular heart disease indicating the need for mechanical repair/replacement or any other structural cardiac surgery (e.g. LV aneurysm resection)
8. Pregnancy
9. Individuals who have declined access to Hospital Episode Statistics for research purposes
10. An inability to understand the languages in which the trial materials are provided

1.15 SAMPLING

Eligibility will be determined by the Heart Team at individual sites. Patients will be identified in the cardiology or cardiac surgery (in person/ hybrid/ virtual) clinics, catheterisation laboratories, Heart Team meetings or wards at each hospital before the index revascularisation procedure where informed consent will be obtained. The benefits and risks of participating in the trial will be explained to the patient, and the patient will have the opportunity to read the Participant Information Sheet (PIS) and Informed Consent Form (ICF) and ask any questions they may have. Patients and carers may attend once or more times, or have subsequent telephone or video calls, to carefully consider their participation. Prior to conducting any trial-related procedures, the patient must provide informed consent to participate by signing the Institutional Review Board / Research Ethics Board (IRB/REB) approved ICF. Patients will be randomised on the day of consent. Recruitment of participants will be guided by the INCLUDE Ethnicity Framework and a STICH3-BCIS4 trial work stream that aims to increase representation from underserved communities as described above.

1.16 SIZE OF SAMPLE

STICH3-BCIS4 is a superiority trial powered for the primary outcome of survival time from cardiovascular hospitalisation and all-cause mortality. Using a time-to-event analysis to detect a HR of 0.7 with a 1:1 allocation ratio, 90% power, and a 2-sided alpha value of 0.05, a total of 414 events are required. Participants will receive a minimum of 4 years follow-up and 630 participants (n=315 in each arm) will be randomised in the UK.

The sample size is based on the following assumptions. **1.** A minimum clinically important treatment effect HR for CABG vs. PCI of 0.7 that is written within the range of treatment effects (0.63 to 0.74) observed in previous pragmatic RCTs of CABG versus PCI that have changed clinical practice (20-22). The proposed effect size was chosen as stakeholders felt that a large benefit would be required to convince clinicians of the benefits of more invasive treatment (CABG) in this high-risk population. **2.** Frequency of death or cardiovascular hospitalisation of 70% at 5 years in the PCI arm, from HES. To

calibrate this outcome, we compared the frequency of death or *heart failure* hospitalisation at 5 years in the STICH-1 matched HES cohort (42%) to event rates in both REVIVED and STICH trials (see Figure 1, from reference (8)). As heart failure hospitalisation is underestimated in HES data, the expected outcome frequencies are consistent. Coding for CV hospitalisation is more accurate and is included in the primary outcome for STICH3-BCIS4. **3.** A total study period of 89 months. **4.** An expected crossover rate of 8% typical for CABG vs. PCI trials; range 7-9%. (6, 7). **5.** Zero attrition due to the use of HES / Office for National Statistics (ONS) data for the primary outcome.

1.17 OUTCOMES

1.17.1 Primary Effectiveness Outcome

Survival time from cardiovascular hospitalisation all-cause mortality: defined in whole days measured as time from randomisation until date of first cardiovascular hospital or death from any cause, whichever happens first. Participants who withdraw or are lost to follow-up will be censored at the date last known to be alive and free from cardiovascular hospitalisation. Participants not having an event at the time of the analysis will be censored at the last date known to be alive and free from cardiovascular hospitalisation.

1.17.2 Secondary Effectiveness Outcomes

- 1.** Overall survival time, defined in whole days measured as time from randomisation until date of death from any cause. Participants who withdraw or are lost to follow-up will be censored at the date last known to be alive. Participants not having an event at the time of the analysis will be censored at the last date known to be alive.
- 2.** Cardiovascular survival time, defined in whole days measured as time from randomisation until date of death from cardiovascular cause. Participants who withdraw or are lost to follow-up will be censored at the date last known to be alive. Participants not having an event at the time of the analysis will be censored at the last date known to be alive. Participants who die from other causes will be censored at date of death.
- 3.** Time until cardiovascular hospitalisation, defined in whole days measured as time from randomisation until cardiovascular hospitalisation. All other participants will be censored at last known follow-up assessment having not had a cardiovascular hospitalisation.

4. Time until heart failure hospitalisation, defined in whole days measured as time from randomisation until heart failure hospitalisation. All other participants will be censored at last known follow-up assessment having not had a heart failure hospitalisation.
5. Time until non-procedural myocardial infarction, defined in whole days measured as time from randomisation until non-procedural myocardial infarction. All other participants will be censored at last known follow-up assessment having not had a non-procedural myocardial infarction.
6. Time until revascularisation other than assigned treatment, defined in whole days measured as time from randomisation until revascularisation. All other participants will be censored at last known follow-up assessment having not had a revascularisation.
7. Time until stroke, defined in whole days measured as time from randomisation until date of stroke. All other participants will be censored at last known follow-up assessment having not had a stroke.
8. Days Alive and Out of Hospital at 90 and 365 days, defined in whole days measured as a continuous variable, calculated as last known date to be alive, minus discharge date following assigned treatment, minus all episodes of hospitalisation (discharge date minus admission date).
9. The number of total (first and recurrent) cardiovascular hospitalisations and heart failure hospitalisations, defined as a count and calculated as the sum of all episodes of hospitalisation with cardiovascular or heart failure cause.
10. Kansas City Cardiomyopathy Questionnaire (KCCQ), derived clinical summary score as a continuous measure collected at discharge and then 3 months and 6 months, and every 6 months thereafter by telephone / ResearchApp®
11. Seattle Angina Questionnaire-7 (SAQ-7), derived overall summary score as a continuous measure collected at discharge and then 3 months and 6 months, and every 6 months thereafter by telephone / ResearchApp®.

1.18 ADVERSE EVENTS OF SPECIAL INTEREST (AESI) WITHIN 30 DAYS OF PCI OR CABG

The following will be collected as AESIs within 30 days of PCI or CABG with the aim of providing reportable data to the Data Monitoring Committee (DMC) at regular meetings ahead of HES data being available.

1. Stroke.
2. New onset renal failure requiring dialysis.
3. Unplanned mechanical circulatory support (intra-aortic balloon pump (IABP), Impella, venoarterial extra corporeal membrane oxygenation (VA ECMO)).
4. Major bleeding requiring reoperation or rehospitalisation.
5. Major vascular complication requiring interventional radiology or surgical intervention.
6. All-cause mortality.

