1.1 THE HEALTH PROBLEM BEING ADDRESSED

Heart failure (HF) affects 1-2% of the population and is increasing in prevalence due to a growing, ageing, more sedentary population, and improved management of acute myocardial infarction (MI) (1, 2). HF causes severe, debilitating symptoms, high rates of mortality, frequent long hospitalisations, and costs the NHS £2 billion per year (2% of the total NHS budget) (3). Coronary artery disease (CAD) is the most common cause of HF, responsible for 52% of cases in patients under 75 years of age, and is the primary cause of HF with reduced ejection fraction (HFrEF) (4, 5).

In the UK, over 20,000 people per year with ischaemic left ventricular dysfunction (iLVSD) and CAD undergo revascularisation with coronary artery bypass grafting (CABG) or percutaneous angioplasty and stents (PCI). However, the choice of revascularisation strategy in HF is not guided by high quality evidence because most randomised controlled trials (RCTs) comparing the effectiveness of CABG versus PCI included small numbers (1%-7%) of people with iLVSD (6, 7). The evidence from these trials may not be generalisable to people with HF; observational analyses suggest that the risks and benefits for CABG (8) and PCI are different in people with – versus people without HF (9). No RCT has compared the effectiveness of PCI and CABG in people with iLVSD. This represents an important unmet need in a high-risk population that experiences all-cause mortality rates of up to 30% at 5 years (8).

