1.2 THE CLINICAL IMPACT OF THE HEALTH PROBLEM

In the UK, this knowledge gap is associated with significant and unwarranted variation in care. The proportion of people with HF undergoing multi-vessel revascularisation who undergo CABG ranges from 30% to 100% across Clinical Commissioning Groups (CCGs) in England. This variation is not attributable to differences in measured cofounders and is associated with significant variation in clinical outcomes; 5-year all-cause mortality in the quartile of CCGs with the lowest CABG: complex

(multivessel) PCI rates were 34%, whereas in the quartile with the highest CABG: PCI rates it was 29%.

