First, as many patients with iLVSD are elderly, clinicians and patients are often unwilling to accept increased short-term risk even if they might eventually achieve long-term benefit given that they have substantially higher rates of adverse events and early mortality post CABG compared to people without iLVSD. **Second**, the completeness and durability of revascularisation will have a greater relative effect on long-term outcome in iLVSD given the severity of disease and resulting higher mortality rate in the longer term versus those without iLVSD (9). A **third** consideration is the duration of follow-up required to derive benefit. In STICH-1, the survival benefit from CABG versus medical therapy was only evident at 10 years (11, 12). **Fourth**, in STICH-1, although the reduction in cardiovascular (CV) mortality was consistent across all age groups, a convincing reduction in all-cause mortality was only evident in patients less than 60 years of age. In the *in-silico* study, sub-group analysis did not demonstrate a significant interaction between the overall treatment effect and age. However, in patients with chronic kidney disease (CKD) or previous stroke the treatment benefit for CABG was not significant, further highlighting the knowledge gap (8). **Fifth**, quality of life is commonly ranked as more important than survival in patients with HF (14, 15). To our knowledge, no study has evaluated this in the context of PCI versus CABG in iLVSD. **Sixth**, contemporary state-of-the-art PCI is associated with improved outcomes compared to historical practices. The STICH-1 trial is over 15 years old, and contemporary PCI approaches have yet to be compared to CABG in patients with iLVSD. **Finally**, there is a current lack of high-quality evidence to evaluate the cost-effectiveness of PCI, compared with CABG, in patients with iLVSD. Given that HF costs the NHS £2 billion per year (2% of the total NHS budget), and that this cost is likely to increase due to an ageing population and lifestyle factors, it is important that such data be generated to ensure the efficient use of scarce NHS resources. Together, these knowledge gaps highlight the unmet need for a high-quality trial of CABG versus PCI in a representative cohort of UK patients with iLVSD.

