1.47 SECONDARY AND TERTIARY OUTCOMES AND SAFETY ANALYSES

Details of the analysis of the secondary outcome measures will be written in the SAP as described above and will follow the same principles as the primary outcome analysis with the exception of outcomes with potentially missing follow-up observations (e.g., PROMS) where a complete case analysis approach will be followed. Secondary outcomes will be reported similarly to the primary outcome using appropriate methodology, point estimates and confidence intervals to compare randomised groups; time to event outcomes using log-rank Kaplan-Meier and proportional hazards models, binary outcomes using logistic regression, continuous outcomes using linear regression or where not normally distributed using appropriate nonparametric methods.

Serious adverse event reporting is described in earlier sections and is largely for safety and ethics monitoring during the trial accrual and follow-up periods prior to statistical analysis taking place. AEs that meet the criteria for reporting as described above will be reported descriptively and summarised between groups based on the safety population (e.g., assigned to groups only if treated and according to treatment received).

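### Cardiovascular survival censors deaths from other causes and is to be summarised by Kaplan-Meier, so each arm's absolute risk of cardiovascular death would read somewhat too high

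*Protocol*

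**What the plan says.** Protocol 1.17.2 item 2 defines cardiovascular survival as "measured as time from randomisation until date of death from cardiovascular cause" and adds: "Participants who die from other causes will be censored at date of death". Items 3 to 7 (cardiovascular and heart failure hospitalisation, non-procedural infarction, revascularisation, stroke) censor every participant without the event at the last follow-up assessment, which by implication includes those who have died.

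Protocol 1.47 carries the principles of the primary analysis over to the secondary outcomes and lists "time to event outcomes using log-rank Kaplan-Meier and proportional hazards models". In the primary analysis (1.46), "Survival estimates will be presented using methods by Kaplan and Meier". The protocol nowhere names cumulative incidence or any other competing-risk estimate. It leaves the details of the secondary analyses to the SAP, which is not at hand.

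**The concern.** A participant who dies of another cause can no longer die of a cardiovascular one. Kaplan-Meier with such deaths censored treats that participant as still exposed to cardiovascular death. The complement of the curve then describes a setting in which other deaths do not happen, not the share of trial participants who die of cardiovascular causes. The curves for cardiovascular and other-cause death would not add up to the all-cause mortality reported as item 1 of the same list.

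Cause-specific mortality matters in this population. The Rationale recalls that in STICH-1 the effect on cardiovascular mortality was consistent across age groups, whereas "a convincing reduction in all-cause mortality was only evident in patients less than 60 years of age". Protocol 1.7 expects the results to inform patients, clinicians and Heart Team discussions, and survival curves are readily read as absolute risks.

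**Working it through.** The protocol states no figure for cardiovascular death, so there is none to reproduce. The 414 events in 1.16 concern the primary outcome, which counts all deaths and is not affected.

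**Inputs from the protocol.** All-cause mortality at 5 years: "all-cause mortality rates of up to 30% at 5 years" (1.1), and 29% and 34% in the regional quartiles (1.2). Participants per arm: 315 (1.16). Longest follow-up: 41 months of recruitment plus 48 months = 89 months, or 7.4 years (1.20).

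**Assumptions.** Cardiovascular share of deaths s = 50-80%; the protocol's mortality applied to the PCI arm; constant hazards; cardiovascular hazard ratio 0.7 for CABG; other-cause hazards equal unless stated.

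**Formulas.** With all-cause mortality m at 5 years, the total hazard is H = -ln(1 - m)/5. The cardiovascular hazard is c = sH and the other-cause hazard is n = (1 - s)H.
- One minus Kaplan-Meier (KM) at time T: 1 - exp(-cT)
- Cumulative incidence (CIF): c/(c + n) × (1 - exp(-(c + n)T))

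**Main case (m = 30%, s = 60%, T = 5).** H = 0.0713, c = 0.0428, n = 0.0285 per year.
- PCI: 1 - KM = 1 - exp(-0.214) = 19.27%; CIF = 0.6 × 30% = 18.00%; excess 1.27 points.
- CABG: c = 0.7 × 0.0428 = 0.0300. 1 - KM = 13.91%; CIF = 12.99%; excess 0.92 points.
- Difference between arms: 5.35 points by KM, 5.01 by CIF; excess 0.34 points.
- Adding up in the PCI arm: other-cause 1 - KM = 1 - exp(-0.0285 × 5) = 13.3%, and 19.3% + 13.3% = 32.6% against 30% all-cause. The two CIFs are 18% + 12% = 30%.

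**Range at 5 years** (percent and points; excesses were rounded after subtraction):

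| m | s | PCI 1 - KM | PCI CIF | Excess | Difference, KM | Difference, CIF | Excess |
|---|---|---|---|---|---|---|---|
| 29% | 50% | 15.74 | 14.50 | 1.24 | 4.44 | 4.10 | 0.34 |
| 29% | 80% | 23.97 | 23.20 | 0.77 | 6.51 | 6.31 | 0.20 |
| 30% | 60% | 19.27 | 18.00 | 1.27 | 5.35 | 5.01 | 0.34 |
| 34% | 50% | 18.76 | 17.00 | 1.76 | 5.22 | 4.75 | 0.48 |
| 34% | 80% | 28.28 | 27.20 | 1.08 | 7.52 | 7.25 | 0.27 |

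In the CABG arm the excess at 5 years runs from 0.57 to 1.28 points. At 7.4 years the PCI-arm excess is 1.5-3.5 points and the excess in the difference is 0.4-0.9 points.

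**Unequal other-cause hazards (m = 30%, 5 years, s = 50-80%).** The excess in the difference is 0.39 to 0.65 points at an other-cause hazard ratio of 0.7, 0.21 to 0.37 at 1.0, 0.04 to 0.10 at 1.3, and -0.08 to -0.09 at 1.5. The sign changes between 1.3 and 1.5.

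**Against sampling error (main case).** For one arm, SE = sqrt(0.18 × 0.82/315) = 2.2 points, so the excess is about 0.58 SE. For the difference, SE = sqrt((0.18 × 0.82 + 0.13 × 0.87)/315) = 2.9 points, so the excess is about 0.12 SE. These SEs ignore censoring before 5 years, so both ratios are upper values.

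**The case against.** The strongest reply is that this is SAP territory. Protocol 1.47 opens with "Details of the analysis of the secondary outcome measures will be written in the SAP", promises appropriate methodology, and mentions Kaplan-Meier only in a short generic list. The SAP may well add a competing-risk estimate. That lowers the weight of the point but does not remove it: the protocol states both the censoring rule and the estimator, and an SAP that simply follows them produces the biased curve.

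It is also true that the censoring sentence is not an error. Censoring other deaths is the usual way to estimate a cause-specific hazard ratio, and both the log-rank test and the Cox model stand.

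A reader might infer more: that the plan overstates the absolute benefit of CABG. The documents do not support that. The protocol commits to no risk difference for cardiovascular death; its comparative measures are the log-rank test and the hazard ratio. An inflated difference requires a real cardiovascular benefit and other-cause hazards that are not much higher after CABG, and the sign reverses when they are high enough. Even in the main case the shift is about 0.12 SE.

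Finally, unbiased absolute mortality is already available from overall survival (item 1), and the 7.4-year figures concern only the earliest recruits, since the stated median follow-up is 5.3 years.

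**Conclusion.** The point holds for the absolute risks only. Followed as written, 1.17.2 item 2 with 1.47 gives cardiovascular death curves whose complement is too high in each arm whenever other deaths occur. On the protocol's 29-34% all-cause mortality, the PCI-arm excess is about 0.8-1.8 points at 5 years and 1.5-3.5 points at 7.4 years. These sizes rest on the assumed 50-80% cardiovascular share and constant hazards; the direction does not. The distortion of the difference between arms is small and can take either sign. The cause-specific test, the hazard ratio and the primary analysis are unaffected. Severity is low: a free improvement.

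**What to change.** In 1.47 (and in the SAP), keep the cause-specific log-rank test and Cox model for cardiovascular death, but present absolute risks by Aalen-Johansen cumulative incidence with non-cardiovascular death as the competing event. Show the cumulative incidence of non-cardiovascular death by arm beside it, so that the two sum to all-cause mortality. Use the same display for the non-fatal outcomes in items 3 to 7, with death as the competing event; no size was worked out for those. The censoring sentence in item 2 can stay, marked as applying to the hazard analysis. The cost is a few lines of wording and standard software output, with no new data beyond the cause of death that item 2 already needs, and no change to any hypothesis test or to the sample size.
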